5.4.4 DLT Terminology Clarifications

- 5.4.4.1 Unless otherwise noted, “clinically relevant” is defined as placing the patient at risk for other toxicity by the judgment of the treating investigator.
- 5.4.4.2 “Optimal supportive care” is defined as standard of care measures that the treating physician deems appropriate and sustainable over multiple cycles of therapy. Specific supportive care guidelines are given below in 5.5. This definition relies upon the clinical judgment of the treating investigator. This may include (but is not limited to) the following:
 - 5.4.4.2.1 Intravenous fluid hydration for dehydration
 - 5.4.4.2.2 Electrolyte supplementation for low electrolytes
 - 5.4.4.2.3 Loperamide for diarrhea
 - 5.4.4.2.4 Antiemetics for nausea
 - 5.4.4.2.5 Skin care for rash
 - 5.4.4.2.6 Printed information as used in standard clinical care)

5.5 Supportive Care Guidelines

Supportive medications to alleviate or mitigate adverse effects of protocol therapy may include the following agents at the discretion of the treating investigator and according to institutional standards of care.

5.5.1 Antidiarrheal Agents

Patients should be instructed to begin loperamide at the earliest signs of a poorly formed or loose stool. Oral loperamide should be prescribed in the following manner: 4 mg at first onset of diarrhea then 2 mg every 2 hours until diarrhea-free for at least 12 hours up to 16 mg daily.

5.5.2 Antiemetic Agents

Drugs such as lorazepam, prochlorperazine, or serotonin antagonists may be used if clinically indicated.

5.5.3 Antihistamines

An antihistamine such as diphenhydramine may be used to manage dermatitis associated with therapy at the discretion of the treating physician.

5.5.4 Anti-diabetic Agents

For patients who develop clinically significant hyperglycemia on study protocol, anti-diabetic therapy and dietary modification are required. The oral anti-diabetic agents, glyburide or metformin, may be instituted at the discretion of the treating physician, assuming no contraindication.

Insulin may be instituted at the discretion of the treating physician to optimize glycemic control. Management of complications of hyperglycemia should be performed by treating physician according to institutional standard practices. All patients who develop clinically significant hyperglycemia on study protocol must receive diabetic teaching and education materials.

(Note: Metformin must be temporarily discontinued for ≥ 48 hours before and after iodinated contrast imaging, with confirmation of stable renal function prior to resuming this agent after contrast exposure.)

5.5.5 Antihyperlipidemic Agents

Patients who develop serum cholesterol > 350 mg/dL and/or triglycerides > 300 mg/dL while on therapy will require medication (assuming no contraindications and with standard precautions as appropriate for the class of agents chosen) and/or dietary modifications at the discretion of the treating investigator.

Concomitant use of pazopanib and simvastatin (Zocor) increases the risk of ALT elevations and should be undertaken with caution and close monitoring. If a subject receiving concomitant simvastatin develops ALT elevations, follow the Guidelines for Management of Treatment Emergent Hepatotoxicity and discontinue simvastatin. Insufficient data are available to assess the risk of concomitant administration of alternative statins and pazopanib.

Pravastatin or rosuvastatin is recommended if LDL and/or total cholesterol are elevated, with or without elevated triglycerides, because these agents are not CYP 3A4 substrates. Atorvastatin may also be used with caution. If tryglycerides alone are elevated, fenofibrate may be considered.

5.5.6 Antihypertensive Agents

Patients who develop blood pressures $\geq 140/90$ mm Hg on at least 2 occasions should be managed with oral antihypertensives including amlodipine, hydrochlorothiazide, or metoprolol by their treating physician.

5.5.7 Diuretics

Diuretics such as furosemide may be used for the management of

periorbital or lower extremity edema at the discretion of the treating physician. Severe episodes of edema, such as congestive heart failure, pleural effusion, ascites, pericardial effusion, or pulmonary edema may require additional measures such as percutaneous drainage or hospitalization.

5.5.8 Electrolyte Supplementation

Electrolytes should be repleted according to standard institutional protocols.

5.5.9 Growth Factors

Erythropoietin or darbopoietin are permitted at the discretion of the treating physician. Filgrastim and PEG-filgrastim (Neulasta) should not be used in place of protocol-specified dose reductions or delays for myelosuppression, nor should they be used prophylactically because of concern for myelosuppression from a prior cycle of chemotherapy.

For treatment of febrile neutropenia, the use of colony-stimulating factors should not be routinely instituted as an adjunct to appropriate antibiotic therapy. The use of granulocyte colony-stimulating factors may be indicated, however, in subjects who have prognostic factors that are predictive of clinical deterioration such as pneumonia, hypotension, multi-organ dysfunction, sepsis syndrome, or fungal infection. Investigators should use discretion in initiating colony-stimulating factors in these settings.

5.5.10 Topical Agents

Topical steroid creams may be used to manage pruritic skin toxicity at the discretion of the treating physician. Non-alcohol-based topical emollients such as Aquaphor may be used for hand-foot syndrome or desquamating rashes. Non-alcohol-based moisturizers may be used for dry skin.

5.5.11 Anti-viral Agents

It is recommended that patients be treated with prophylactic Valtrex (valacyclovir hydrochloride) 500 mg daily, however final decisions regarding this will be up to treating physician discretion.

5.6 Concomitant Medications

Concomitant medications are any prescription medications or over-the-counter preparations used by the patient within 28 days of initiating study treatment, during study treatment, and up to 28 days following study termination.

All patients will receive prophylaxis with trimethoprim-sulfamethaxazole double strength (sulfamethoxazole 800 mg and trimethoprim 160 mg) by mouth 3 times a week. If a patient is allergic to this antibiotic it can be substituted per physician recommendation. The details of all concurrent medications including vitamins

and alternative therapies will be recorded on the electronic case report forms (eCRFs).

All medications must be reviewed for potential interaction with study drug therapy. All concomitant medications and blood products, as well as supportive interventions (such as analgesic use, paracentesis, etc.) received by patients from screening until the end of study visit will also be recorded on the appropriate eCRFs.

Concomitant use of pazopanib and simvastatin (Zocor) increases the risk of ALT elevations and should be undertaken with caution and close monitoring. If a subject receiving concomitant simvastatin develops ALT elevations, follow the Guidelines for Management of Treatment Emergent Hepatotoxicity and discontinue simvastatin. Insufficient data are available to assess the risk of concomitant administration of alternative statins and pazopanib (see section 8.2.8 and Appendix II).

Concomitant use of any of the following is PROHIBITED while on this study:

- 5.6.1** Subjects may not receive other anti-cancer therapy [cytotoxic, biologic, radiation, or hormonal (other than leuprolide or other GnRH agonists)] while on treatment in this study.
- 5.6.2** Medications that inhibit CYP3A4 may result in increased plasma pazopanib concentrations; therefore, co-administration of strong CYP3A4 inhibitors is PROHIBITED beginning 28 days prior to the first dose of study drug until discontinuation from the study. Strong CYP3A4 inhibitors include (but are not limited to):
 - 5.6.2.1** Antibiotics: clarithromycin, telithromycin, troleandomycin
 - 5.6.2.2** HIV: protease inhibitors (ritonavir, indinavir, saquinavir, nelfinavir, amprenavir, lopinavir)
 - 5.6.2.3** Antifungals: itraconzaole, ketoconazole, voriconazole
 - 5.6.2.4** Antidepressants: nefazodone.

Please refer to Appendix II for a more complete listing of these agents. Those who have taken medications that are known strong inducers or inhibitors of CYP3A4 within 28 days before registration will be excluded from the study. Please refer to Section 8 for details regarding drug interactions for temozolomide and pazopanib.

5.7 Toxicity Management and Dose Modifications

5.7.1 Assessing toxicity

Toxicity will be graded according to the NCI CTCAE version 4.03. Toxicity will be formally assessed at scheduled clinic follow up appointments every one to two weeks, as well as by investigator review of weekly laboratory testing; in the interim, toxicity may be assessed via patient contact with the study coordinator and/or clinical staff should new symptoms arise between visits.

5.7.2 Treatment rules for toxicity for phase I AFTER the DLT period

Protocol therapy will be delayed, dose-reduced, or discontinued based upon the most severe toxicity encountered in the previous cycle and/or laboratory parameters on the scheduled day of treatment. For *treatment-related* delays in protocol therapy, the longest permitted interval of treatment interruption is 28 days to remain on study. For *non-treatment-related* delays, the maximum permitted interval is 8 weeks to remain on study. General principles of toxicity management are as follows:

- 5.7.2.1** Temozolomide and pazopanib will be dose-adjusted according to attribution of toxicity. In equivocal cases, the decision may be made by treating investigator with approval from the DMC.
- 5.7.2.2** Individual dose modifications will be made according to the system showing greatest degree of toxicity using NCI CTCAE version 4.03.
- 5.7.2.3** Asymptomatic changes in laboratory values require dose modification only if assessed to be treatment-related, clinically relevant, and represent a change of ≥ 2 grades from baseline.
- 5.7.2.4** If toxicity occurs, supportive care medications should be applied to ameliorate signs and symptoms (refer to Section 5.5) before toxicity grade is determined.
- 5.7.2.5** A patient will be removed from protocol therapy if either of the two study drugs is discontinued.
 - 5.7.2.5.1** Temozolomide will be discontinued if it is not tolerated at a dose of 50 mg/m² daily.
 - 5.7.2.5.2** Pazopanib will be discontinued if it is not tolerated at a dose of 200 mg daily.
- 5.7.2.6** A patient will be removed from protocol therapy if treatment with either of the two study drugs is held for toxicity for longer than 28 days (1 cycle).
- 5.7.2.7** Once a dose has been reduced for toxicity, it should not be re-escalated.
- 5.7.2.8** In obese patients, all dosing is to be determined by the patient's actual body weight.
- 5.7.2.9** If there is more than one indication for dose modification, use the more strict dose modification (i.e. modify according to the most severe toxicity).

5.7.3 Patient dose level adjustments for toxicity in Phase II

For patients enrolled in the phase II portion, the following adjustments should be made in the appropriate drug (depending on attribution of toxicity) based upon the patient's starting dose and the guidelines below in Section 5.7.4. As stated above, if either study drug is discontinued, a patient will be removed from study.

Table 4: Patient Dose Level Adjustments for Toxicity: Temozolomide

Patient Temozolomide Dose Level	Temozolomide Dose Modification
Level 1: 150mg/m ² per day p.o.	↓ 100 mg/m ² per day p.o.
Level -1: 100 mg/m ² per day p.o.	↓ 75 mg/m ² per day p.o.
Level -2: 75mg/m ² per day p.o.	↓ 50 mg/m ² per day p.o
Level -3: 50mg/m ² per day p.o.	Discontinue

Table 5: Patient Dose Level Adjustments for Toxicity: Pazopanib

Patient Pazopanib Dose Level	Pazopanib Dose Modification
Level 3 800 mg per day p.o.	↓ 600 mg per day p.o.
Level 2 600 mg per day p.o.	↓ 400 mg per day p.o.
Level 1 400 mg per day p.o.	↓ 200 mg per day p.o.
Level -1 200 mg per day p.o.	Discontinue

5.7.4 Dose modifications for toxicity

Held doses of either drug will be considered as omitted. For example, if pazopanib is held for one week starting cycle 2 day 8, the next dose of temozolomide the following week will still be considered cycle 2, day 15 (rather than delaying the cycle and repeating the day 8 dose).

5.7.4.1 Temozolomide dose modifications

Please refer to Table 6 below for a summary of dose modifications for temozolomide for both hematologic and non-hematologic toxicities. Toxicities that are judged to be unrelated to study drug will not require dose modifications.

Table 6: Summary of Hematologic & Non-Hematologic Dose Modifications for Temozolomide

Toxicity	Grade (NCI CTCAE v 4.03)	Temozolomide (TMZ) Adjustment
HEMATOLOGIC		
Neutropenia	Grade 1 ANC 1500 to < 2000/mm ³	No change
	Grade 2 ANC 1000 to < 1500/mm ³	No change

Toxicity	Grade (NCI CTCAE v 4.03)	Temozolamide (TMZ) Adjustment
	Grade 3 ANC 500 to < 1000/mm ³	Hold TMZ, repeat CBC weekly until \leq grade 2, then decrease 1 level
	Grade 4 ANC < 500/mm ³	Hold TMZ, repeat CBC weekly until \leq grade 2, then decrease 1 level
Lymphopenia	Any Grade	No dose reductions
Thrombocytopenia	Grade 1 Plts 75,000 to < LLL/mm ³	No change
	Grade 2 Plts 50,000 to 75,000/mm ³	No change
	Grade 3 Plts 25,000 to < 50,000/mm ³	Hold TMZ, repeat CBC weekly until \leq grade 2, then decrease 1 level
	Grade 4 Plts < 25,000/mm ³	Hold TMZ, repeat CBC weekly until \leq grade 2, then decrease 1 level
Anemia	Any Grade	No dose reductions or delays will be performed for anemia; transfusions and/or growth factor support may be used at the discretion of the investigator
ALL OTHER NON-HEMATOLOGIC TOXICITY		
Other toxicity (despite optimal care)	Grade 1	No change
	Grade 2	No change
	Grade 3	Hold TMZ until \leq grade 2, then decrease 1 level
	Grade 4	Discontinuation of therapy and removal from study

5.7.4.2 Pazopanib dose modifications

There will be no dose modifications of pazopanib for hematologic toxicity of any grade. There will be no dose modifications for grade 1 or 2 non-hematologic toxicities. For grade 3 and/or 4 non-hematologic toxicities, please see Table 7 below.

Table 7: Summary of Hematologic & Non-Hematologic Dose Modifications for Pazopanib

Toxicity	Grade (NCI CTCAE v 4.03)	Pazopanib (PAZ) Adjustment
GASTROINTESTINAL (EXCLUDING HEPATIC DYSFUNCTION)		
Nausea/vomiting, constipation, or mucositis (despite optimal supportive care)	Grade 1	No change
	Grade 2	No change
	Grade 3	Hold PAZ and monitor until \leq grade 2, then decrease 1 level
	Grade 4	Hold PAZ and monitor until \leq grade 2, then decrease 1 level
Diarrhea (despite optimal supportive care)	Grade 1	No change
	Grade 2	No change
	Grade 3	Hold PAZ and monitor until \leq grade 2, then decrease 1 level
	Grade 4	Hold PAZ and monitor until \leq grade 2, then decrease 1 level
CARDIOVASCULAR AND VASCULAR		
Hypertension	Scenario A: Asymptomatic and persistent SBP of \geq 140 and $<$ 170 mmHg, or DBP \geq 90 and $<$ 110 mmHg, or a clinically significant increase in DBP of 20 mmHg (but still below 110 mmHg)	
 1. Continue PAZ at the current dose. 2. Adjust current or initiate new antihypertensive medication(s). 3. Titrate antihypertensive medication(s) during next 2 weeks as indicated to achieve well-controlled BP. If BP is not well-controlled within 2 weeks, consider referral to a specialist and go to Scenario B.
	Scenario B: Asymptomatic SBP \geq 170 mm Hg or DBP \geq 110 mmHg, or failure to achieve well-controlled BP within 2 weeks under Scenario A.	
 1. Consider reducing or interrupting PAZ, as clinically indicated. 2. Adjust current or initiate new antihypertensive medication(s). 3. Titrate antihypertensive medication(s) during next 2 weeks as indicated to achieve well-controlled BP. 4. Once BP is well-controlled, restart PAZ at 1 dose level (200 mg) lower if PAZ was interrupted.

Toxicity	Grade (NCI CTCAE v 4.03)	Pazopanib (PAZ) Adjustment
	Scenario C: Symptomatic hypertension or recurring SBP \geq 170 mmHg or DBP \geq 110 mmHg, despite modification of hypertensive medication(s)	Interrupt PAZ. Adjust current or initiate new antihypertensive medication(s). Titrate antihypertensive medication(s) during next 2 weeks as indicated to achieve well-controlled BP. Referral to a specialist for further evaluation and follow-up is recommended. Once BP is well-controlled, restart PAZ at 1 dose level (200 mg) lower if PAZ was interrupted.
	Scenario D: Refractory hypertension unresponsive to above interventions.	Discontinue PAZ and follow-up per protocol.
Arterial Thrombus [Cardiac ischemia/infarction, CNS ischemia (TIA, CVA), any peripheral or visceral arterial ischemia/thrombus]	\geq Grade 3	Discontinue PAZ
Venous Thrombus	Grade 3/4	Hold PAZ. If the planned duration of full-dose anticoagulation is <2 week, PAZ should be held until this is over If the planned duration of the full-dose anticoagulation is >2 weeks, PAZ can be resumed once criteria are met: Subject must have in-range INR (usually 2-3) on a stable dose of warfarin or be on a stable dose of heparin and the subject must not have pathologic conditions that carry high risk of bleeding. If thromboembolic disease worsens, discontinue PAZ
DERMATOLOGIC		
Hand-foot syndrome (despite optimal supportive care)	Grade 1	No change
	Grade 2	No change
	Grade 3	Hold PAZ until \leq grade 2, then decrease 1 level
	Grade 4	Hold PAZ until \leq grade 2, then decrease 1 level

RENAL AND URINARY		
Proteinuria	UPC < 3	Continue PAZ at the current dose; monitor as clinically indicated.
	UPC \geq 3 or 24-hr urine protein \geq 3g	
 1. Interrupt PAZ 2. Weekly UPC or 24-hr urine protein monitoring until UPC is < 3 or 24-hr urine protein is < 3g. Then restart PAZ at 1 dose level (200 mg) lower. 3. If UPC ≥ 3 or 24-hr urine protein ≥ 3g recurs, repeat steps 1 and 2. 4. If UPC ≥ 3 or 24-hr urine protein ≥ 3g recurs and the PAZ dose can no longer be reduced, discontinue PAZ and follow-up per protocol.
CARDIAC		
Prolongation of QTc Interval	QTc $\geq 480 < 500$ msec	Continue PAZ; monitor as clinically indicated.
	QTc ≥ 500 msec	Discontinue PAZ and follow-up per protocol.
HEMORRHAGE/BLEEDING		
Hemorrhage/Bleeding	Grade 1	
For hemoptysis, interrupt PAZ and contact the NOVARTIS Study Physician to discuss whether further treatment with PAZ is appropriate.
 
For other Grade 1 hemorrhage/bleeding events, continue PAZ at the current dose; monitor as clinically indicated.

	Grade 2	
 1. If pulmonary or GI bleed (other than hemorrhoidal bleeding), discontinue PAZ and continue follow-up per protocol. Otherwise, interrupt PAZ until resolved to \leq Grade 1. 2. Restart PAZ; consider reducing dose and monitor as clinically indicated.
	Grade 3 or 4 or Recurrent \geq Grade 2 event after dose interruption/reduction	Discontinue PAZ and follow-up per protocol.
ALL OTHER NON-HEMATOLOGIC TOXICITY		
Other toxicity (despite optimal care)	Grade 1	No change
	Grade 2	No change
	Grade 3	Hold PAZ and monitor until \leq grade 2, then decrease 1 level
	Grade 4	Discontinue PAZ

HEPATIC DYSFUNCTION	
Event	Dose Modification Algorithms
(A). ALT of $\leq 3.0 \times$ ULN	Continue pazopanib at current dose with full panel LFTs Error! Reference source not found. monitored as per protocol.
(B). ALT $>3.0 \times$ ULN to $\leq 8.0 \times$ ULN without bilirubin elevation (defined as total bilirubin Error! Reference source not found. $<2.0 \times$ ULN or direct bilirubin $\leq 35\%$) and without hypersensitivity symptoms (e.g., fever, rash)	Liver Event Monitoring Criteria: (1) Continue pazopanib at current dose levels. (2) Monitor subject closely for clinical signs and symptoms; perform full panel LFTs ^a weekly or more frequently if clinically indicated until ALT/AST is reduced to Grade 1.

	
1st occurrence – Liver Event Interruption Criteria Error! Reference source not found.:
 
(1) Interrupt pazopanib until toxicity resolves to \leqGrade 1 or baseline. Report the event to NOVARTIS as an SAE within 24 hours of learning of its occurrence and complete the eCRF liver event forms. Make every reasonable attempt to have subjects return to the clinic within 24 to 72 hours for repeat liver chemistries and liver event follow up assessments.
 
(2) Liver imaging and other laboratory investigations should be considered as clinically appropriate.
 
(3) Monitor subject closely for clinical signs and symptoms; perform full panel LFTs ^a weekly or more frequently if clinically indicated until ALT/AST is reduced to Grade 1.
 
(4) If the potential benefit for reinitiating pazopanib treatment is considered to outweigh the risk for hepatotoxicity, then reintroduce pazopanib at a reduced dose and measure serum liver tests weekly for 8 weeks..^d
 
Re-treatment may be considered if ALL following criteria are met:
 
- ALT/AST reduced to Grade 1- Total bilirubin $<1.5 \times$ ULN or direct bilirubin $\leq 35\%$- No hypersensitivity signs or symptoms- Subject is benefiting from therapy. 
If approval for re-treatment is granted, the subject must be re-consented (with a separate informed consent specific to hepatotoxicity).
 
Recurrence – Liver Event Stopping Criteria Error! Reference source not found.:
 
Discontinue pazopanib permanently and monitor subject closely for clinical signs and symptoms; perform full panel LFTs ^a weekly or more frequently if clinically indicated until ALT/AST is reduced to Grade 1. At the time of the recurrence, complete the eCRF liver event forms.

--	---

	
Liver Event Stopping CriteriaError! Reference source not found.:
 
(1) Discontinue pazopanib immediately, report the event to NOVARTIS as an SAE within 24 hours of learning of its occurrence, and complete the eCRF liver event forms. Make every reasonable attempt to have subjects return to the clinic within 24 hours for repeat liver chemistries and liver event follow up assessments.
 
(2) Consult a gastroenterologist / hepatologist, collect PK sample and perform the following assessments to identify potential co-factors:
 
 - Eosinophil count - Viral serology for hepatitis A, B, C and E, cytomegalovirus, Epstein-Barr virus (IgM antibody, heterophile antibody, or monospot testing) - Anti-nuclear antibody, anti-smooth muscle antibody, Type 1 anti-liver kidney microsomal antibodies. - Serum creatinine phosphokinase for possible muscle injury caused LFT elevation - Liver imaging - Consider toxicological blood screen for possible contributing chemical/medical entities 
(3) Monitor subject closely for clinical signs and symptoms; record the appearance or worsening of clinical symptoms of hepatitis, or hypersensitivity, such as fatigue, nausea, vomiting, right upper quadrant pain or tenderness, fever rash or eosinophilia as relevant on the AE report form. Perform full panel LFTs^a weekly or more frequently if clinically indicated until LFTs are reduced to Grade 1.

For isolated total bilirubinError! Reference source not found. elevation without concurrent ALT increases (defined as ALT <3 X ULN).
	
(1) Isolated hyperbilirubinemia (i.e., in the absence of elevated ALT or other signs/symptoms of liver injury) does not require dose modification. Pazopanib inhibits UGT1A1 and OATP1B1, which can cause elevation of indirect (unconjugated) bilirubin in the absence of liver injury.
 
(2) If bilirubin is >1.5 x ULN in the absence of ALT elevation, fractionation of bilirubin elevation should be performed. If bilirubin is >35% direct (conjugated), further evaluation for underlying cause of cholestasis should be performed.

- a. Full panel LFTs include: AST, ALT, alkaline phosphatase, GGT, and total bilirubin. Coagulation tests should be performed as clinically indicated.
- b. Serum bilirubin fractionation should be performed if testing is available. If testing is unavailable and a subject meets the criterion of total bilirubin $>1.5 \times$ ULN, then the event should be promptly reported as an SAE.
- c. When a liver chemistry event meets the Liver Event Interruption Criteria, or Liver Event Stopping Criteria, blood samples should be obtained for PK and for clinical laboratory testing by the central laboratory (Liver Event Kits will be provided for this purpose).
- d. Please refer to Investigator's Brochure, Summary of Data and Guidance for Investigator, Warnings and Precautions, Hepatic Effects for information about rechallenge dose.

Abbreviations: ALT alanine aminotransferase; AST aspartate aminotransferase; eCRF electronic case report form; IP investigational product; LFT liver function tests; PK pharmacokinetics; SAE serious adverse event; ULN upper limit of normal

5.7.4.5 For any toxicity (regardless of grade), despite optimal supportive care, that is felt by the treating investigator to represent a risk to the patient's safety, additional dose reduction, treatment delay, or treatment discontinuation is permitted at the discretion of the treating investigator with approval from the Principal Investigator and DMC.

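### Section 5.7.4.2 rules out pazopanib changes for grade 1 or 2 non-hematologic toxicity, but the bleeding rows of Table 7 require interruption or discontinuation for some of these events

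*Combined protocol and SAP*

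**What the plan says.** The lead-in to Section 5.7.4.2 of the combined protocol and SAP gives a general rule for pazopanib: "There will be no dose modifications for grade 1 or 2 non-hematologic toxicities". The next sentence limits when the table is consulted: "For grade 3 and/or 4 non-hematologic toxicities, please see Table 7 below".

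The Hemorrhage/Bleeding rows of Table 7, in the same subsection, give instructions at the lower grades:

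- Grade 1: "For hemoptysis, interrupt PAZ and contact the NOVARTIS Study Physician". Other grade 1 bleeds continue at the current dose.
- Grade 2, pulmonary or GI: "If pulmonary or GI bleed (other than hemorrhoidal bleeding), discontinue PAZ and continue follow-up per protocol".
- Grade 2, other sites: "Otherwise, interrupt PAZ until resolved to" grade 1 or lower, then restart and consider a lower dose.
- Recurrent bleeding of grade 2 or higher, described as a "Grade 2 event after dose interruption/reduction", shares a row with grade 3 and 4 bleeding. The action is discontinuation.

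Stopping pazopanib has a further consequence. For phase I after the DLT period, Section 5.7.2.5 says: "A patient will be removed from protocol therapy if either of the two study drugs is discontinued". For phase II, Section 5.7.3 says: "if either study drug is discontinued, a patient will be removed from study".

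**The concern.** The sentence and the table give opposite instructions for the same event, and the sentence tells readers that they need the table only from grade 3 upward. The gap is widest for a grade 2 GI or pulmonary bleed. Under the sentence the patient stays on a VEGFR inhibitor. Under the table the drug stops for good and the patient leaves protocol therapy or the study. Five sites apply these rules, so the same bleed could be handled in two ways. What is at stake is patient safety and consistent conduct between sites, not the response-rate analysis.

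**Working it through.** The plan has no figure of its own on this point to reproduce. The check is a comparison of text, followed by a rough estimate of how often the conflict could arise.

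**1. Sentence against table**

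| Event | Lead-in sentence | Table 7 | Agree? |
|---|---|---|---|
| Grade 1 hemoptysis | No modification | Interrupt | No |
| Other grade 1 bleed | No modification | Continue | Yes |
| Grade 2 pulmonary or GI bleed (not hemorrhoidal) | No modification | Discontinue | No |
| Other grade 2 bleed | No modification | Interrupt, restart, consider reduction | No |
| Recurrent grade 2 bleed after interruption or reduction | No modification | Discontinue | No |

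**2. Readings that might reconcile them**

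- *Bleeding counts as hematologic.* The first sentence of 5.7.4.2 rules out modification for hematologic toxicity at every grade, so the conflict would widen. The table heading after the bleeding rows covers all other non-hematologic toxicity, which places bleeding on the non-hematologic side.
- *Modification means reduction only.* Table 7 is titled as a summary of dose modifications and lists holds and discontinuations. Its grade 2 bleeding row also mentions a lower dose.
- *Another clause covers it.* Section 5.7.4.5 permits changes at any grade, but only at the investigator's discretion and with approval. Section 5.8.1.4.3 and the lead-in to 5.8.2 also rest on clinical judgment. A permission does not reconcile a prohibition with a directive. Section 5.8.2.9 requires removal when a toxicity calls for stopping either drug, but whether a grade 2 bleed calls for that is the open question.

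Appendix V records that Amendment 4 added the hemorrhage modifications to Table 7. The entry mentions no change to the lead-in, which probably explains the mismatch.

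**3. Rough size**

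Inputs: n = 27, the phase II maximum (Section 9.2.1); any-grade bleeding of 13% on pazopanib and 5% on placebo in the renal cell trial (Section 1.4.2); pulmonary hemorrhage and GI hemorrhage each at least 1 in 1000 and under 1 in 100 (Section 8.2.10.3). Assumption: these rates carry over to the combination and to this population. The expected number is n × p, and the chance of at least one event is 1 − (1 − p)^n.

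Bleeding of any grade and site:

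- 13%: 27 × 0.13 = 3.51 patients; 1 − 0.87^27 = 0.977.
- 5%: 27 × 0.05 = 1.35 patients; 1 − 0.95^27 = 0.750.

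Pulmonary or GI bleeding of any grade, assuming that the two do not overlap:

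- Low end, 0.001 + 0.001 = 0.002: 27 × 0.002 = 0.054 patients; 1 − 0.998^27 = 0.053.
- High end, under 0.01 + 0.01 = 0.02: under 27 × 0.02 = 0.54 patients; under 1 − 0.98^27 = 0.420.

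The first pair are ceilings at the assumed rates. They include bleeds of grade 3 and higher, and grade 1 bleeds where sentence and table agree. The second pair also includes grade 3 and higher.

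**The case against.** The strongest reply is that the intent is plain. The table sits directly below the sentence and has its own grade 1 and 2 bleeding rows. Its residual row for other non-hematologic toxicity repeats the no-change rule at grades 1 and 2, so bleeding reads as a specific exception to a general default. Section 10.3 also sends sites to Table 7 with no grade limit, and Section 5.7.3 points phase II sites to the whole of 5.7.4. High-intensity monitoring with DMC oversight (Sections 10.0 and 11.6) makes undetected divergence less likely. Sections 3.3.7, 3.3.15 and 3.3.16 exclude patients at raised risk of GI or pulmonary bleeding, so the quoted rates may be too high. The any-grade figures do not measure the events in conflict.

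Much of this stands. It lowers the chance of harm, and the any-grade figures should be read only as ceilings. The eligibility argument is not one-sided, since Section 3.2.9.6 admits patients on stable anticoagulation. But none of it changes the text. The only stated scope for Table 7 within 5.7.4.2 is grade 3 and 4, and a reader has to infer an exception that the sentence does not make.

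**Conclusion.** The inconsistency is real, and it concerns a working safety rule. Four of the five lower-grade bleeding situations in Table 7 contradict the sentence, and no other clause resolves them. The continue-versus-discontinue conflict is uncommon: at most about half a patient is expected among 27, even at the top of the listed bands. The interruption conflict is probably more frequent, but the documents give no rate for it. These sizes rest on monotherapy, all-grade rates carrying over to this trial. The point should be corrected even though most sites would probably apply the table. Sample size, alpha and power are unaffected.

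**What to change.** Keep the sentence "There will be no dose modifications for grade 1 or 2 non-hematologic toxicities" and add to it: except as specified in Table 7, including hemorrhage/bleeding. Change the following sentence so that it refers to Table 7 for all grades of non-hematologic toxicity. Tell sites in a short memo that the bleeding rows govern.

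The cost is one clause and one cross-reference at the next amendment, plus the memo. The dose rules in Table 7, Section 5.8.2, the design and data collection stay as they are.
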